**Table 2 iPFS Definition**

iPFS		
Situation	Date of Event or Censor	Outcome
No evaluable post-baseline imaging assessments, no death	Date of first dose (Day 1)	Censor
Participant did not receive new anti-cancer therapy (ACT):		
iCPD	First date where iUPD criteria are met	Event
No iCPD, but death recorded on eCRF	Date of death	Event
No iCPD nor death and not in one of the following cases : a) if the participant stops protocol treatment because they were not judged to be clinically stable, b) no further response assessments are done (because of participant refusal, protocol non-compliance, or participant death); c) the next timepoint responses are all iUPD, and iCPD never occurs;	Date of last radiological assessment	Censor
No iCPD nor death and is in one of the following cases : a) if the participant stops protocol treatment because they were not judged to be clinically stable, b) no further response assessments are done (because of participant refusal, protocol non-compliance, or participant death); c) the next timepoint responses are all iUPD, and iCPD never occurs;	First date where iUPD criteria are met	Event
Participant received new anti-cancer therapy (ACT):		
No progression before new ACT	Date of last radiological assessment before start of new anti-cancer therapy	Censor
iCPD before new ACT	First date where iUPD criteria are met	Event
iUPD before new ACT and not in one of the following cases: a) if the participant stops protocol treatment because they were not judged to be clinically stable, b) no further response assessments are done (because of participant refusal, protocol non-compliance, or participant death); c) the next timepoint responses are all iUPD, and iCPD never occurs;	Date of last radiological assessment before start of new anti-cancer therapy	Censor
Table continued on next page		

iPFS		
Situation	Date of Event or Censor	Outcome
iUPD before new ACT and is in one of the following cases : a)if the participant stops protocol treatment because they were not judged to be clinically stable, b) no further response assessments are done (because of participant refusal, protocol non-compliance, or participant death); c) the next timepoint responses are all iUPD, and iCPD never occurs;	First date where iUPD criteria are met	Event
Missed <math>\geq 2</math> scheduled radiological assessments		
If last assessment prior to missing $\geq 2$ scans is iUPD	First date where iUPD criteria are met	Event
If last assessment prior to missing $\geq 2$ scans is not iUPD and no progression or death after missing $\geq 2$ scans	Date of last radiological assessment	Censor
No post-baseline tumor imaging prior to missing 2 scans and progression or death after missing $\geq 2$ scans	Date of first dose (Day 1)	Censor
No post-baseline tumor imaging prior to missing 2 scans and no progression or death after missing $\geq 2$ scans	Date of last radiological assessment	Censor
If radiographical progression or death occurs after missing 2 scheduled radiological assessments and last assessment prior to missing $\geq 2$ scans is not iUPD	Date of last radiological assessment before missing 2 scans	Censor

iPFS = Date of Event or Censor – Date of First Dose +1

Missing 2 scheduled imaging assessments:

Missing 2 scheduled imaging assessments is defined as the gap between two imaging assessments as more than 140 days (2.5 times the scheduled imaging assessment interval (2.5 x 56 days)). Imaging assessments after first iUPD will be excluded from PFS derivation.

Note: Participant cannot be censored at “NE”. If NE is the only previous assessment, then iPFS will be censored at Day 1.

To apply the cut-off date to iPFS is to exclude those tumor assessments after cut-off date and anti-cancer therapy date after cut-off date in the analysis.

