9.4.2.3 Analysis of Secondary Endpoints

Objective Response Rate per RECIST v1.1 (ORR):

ORR is defined as the proportion of participants for each dose level whose best overall response is rated as CR or PR per RECIST v1.1. The same analysis used for the primary endpoint as described in [Section 9.4.2.1.1 Primary Analysis] will be conducted for the following:

- ORR with confirmed response by independent central review
- ORR with unconfirmed response by independent central review
- ORR with confirmed response by investigator assessment
- ORR with unconfirmed response by investigator assessment

Disease Control Rate per iRECIST (iDCR):

iDCR is defined as the proportion of participants for each dose level whose best overall response is rated as confirmed iCR, iPR or stable disease (iSD) per iRECIST. iDCR for dose level will be calculated and its 95% confidence interval will be constructed by Clopper-Pearson method by independent central review and investigator assessment.

Disease Control Rate per RECIST v1.1 (DCR):

DCR is defined as the proportion of participants for each dose level whose best overall response is rated as confirmed CR, PR or SD per RECIST v1.1. DCR by dose level will be calculated and its 95% confidence interval will be constructed by Clopper-Pearson method by independent central review and investigator assessment.

Overall Survival (OS):

OS is defined as the time from the date of first dose until the date of death from any cause (death date - first dose date + 1). For a participant who is not known to have died by the end of study follow-up, OS is censored at the date of last contact (date of last contact - first dose date + 1). The distribution of OS will be estimated for each dose level using Kaplan-Meier methodology.

Progression-free Survival per iRECIST (iPFS):

iPFS is defined as the time from the start of the study treatment until death from any cause or radiographic disease progression assessed per iRECIST by independent central review and investigator assessment, whichever occurs first. The distribution of iPFS will be estimated for each dose level using Kaplan-Meier methodology.

Progression-free Survival per RECIST v1.1 (PFS):

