### 5.1.2.5 Secondary Efficacy Endpoint: Progression-free Survival per iRECIST (iPFS)

iPFS is defined as the time from the date of first dose until death from any cause or radiographic disease progression assessed per iRECIST by investigator assessment.

If unconfirmed disease progression per iRECIST (iUPD) occurs but iSD, iPR, or iCR is observed any time subsequent to iUPD, iUPD status will be disregarded for determination of iPFS.

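### SAP Table 2 (iPFS): two rows require no death yet list participant death in case (b), so unconfirmed progression followed by death is dated inconsistently across the table

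*SAP*

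**What the plan says.** SAP section 5.1.2.5 opens: "iPFS is defined as the time from the date of first dose until death from any cause or radiographic disease progression assessed per iRECIST". The text under it says that an iUPD is disregarded if stable disease or response follows. It says nothing about iUPD followed by death. Protocol section 9.4.2.3 uses nearly the same definition ("iPFS is defined as the time from the start of the study treatment until death from any cause or radiographic disease progression assessed per iRECIST"), takes the earlier of the two events, and does not say whether an unconfirmed progression counts.

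Table 2 then assigns dates. These rows matter here:

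- No new therapy, death row: "No iCPD, but death recorded on eCRF". Date of death, event. There is no condition on an earlier iUPD.
- No new therapy, censoring row: "No iCPD nor death and not in one of the following cases". Last radiological assessment, censored.
- No new therapy, iUPD row: "No iCPD nor death and is in one of the following cases". First iUPD date, event.
- Case (b), repeated in both of the last two rows: "no further response assessments are done (because of participant refusal, protocol non-compliance, or participant death".
- New therapy, iUPD row: "iUPD before new ACT and is in one of the following cases", with the same case (b) but no condition excluding death. First iUPD date, event.
- Missed scans: "If last assessment prior to missing $\geq 2$ scans is iUPD". First iUPD date, event, again with no exclusion for death.

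No order of precedence among the rows is given. SAP section 6.4.2.5 limits the iPFS analysis to a data listing.

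**The concern.** The case list shows that the authors had in mind a participant whose scans stop after iUPD because of death. The header of the same row shuts that participant out. One of the two phrases cannot be intended, and the table does not say which.

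The literal result is also hard to defend. Among participants with iUPD, no confirmation and no new therapy, one who refuses further imaging has the event at iUPD, while an otherwise identical one who dies has it later. Death after iUPD therefore lengthens iPFS. In addition, a living participant already dated at iUPD under case (b) or (c) would move to the death date if a death were recorded later. That can happen, because SAP section 2.2 plans telephone survival follow-up for up to 1 year.

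At stake is the listed iPFS value for each such participant. It depends on how a programmer resolves the wording.

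**Working it through.** The plan states no figure for this point. The check applies the rows of Table 2 to one defined participant.

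**Inputs**
- iPFS = date of event or censoring − date of first dose + 1 (Table 2).
- Scans every 56 days. A gap counts as two missed scans if it exceeds 2.5 × 56 = 140 days (note to Table 2), which reproduces.
- Confirmatory scan for progression at least 4 and at most 8 weeks after progression is first seen (protocol section 7.1).
- Assumed dates for illustration: iUPD 56 days after first dose, so iPFS day 56 + 1 = 57; no new therapy; no later scan; death at various times.

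**Step 1. Which rows does this participant meet?**
Taken literally, the no-death header closes both the censoring row and the iUPD row. Only the death row is left, and the death clause in case (b) has no effect. If the clause is given effect against its header, the iUPD row opens as well.

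**Step 2. Dates**

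| Days from first dose to death | Death row | Case (b), if given effect | Difference |
|---|---|---|---|
| 70 | 70 + 1 = 71 | 57 | 14 days |
| 112 | 112 + 1 = 113 | 57 | 56 days |
| 190 | 190 + 1 = 191 | 57 | 134 days |
| 206 | 206 + 1 = 207 | 57 | 150 days |

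The outcome is an event in every cell.

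**Step 3. Missed-scans row**
In the last line the interval from the iUPD scan to death is 206 − 56 = 150 days, which exceeds 140. If the gap may run from last scan to death, this row gives day 57 while the death row gives day 207, even on the literal reading. That step is an assumption: the note defines the gap between two scans, although the last row of Table 2 does speak of death after missing two scans.

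**Step 4. Comparison with refusal**
Same iUPD, scans refused, participant alive: 57 days, event. Same iUPD, death 112 days after first dose, literal reading: 113 days, event. The participant who died is credited with 113 − 57 = 56 more days.

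**Step 5. Comparison with the new-therapy block**
For iUPD, then new therapy, then death with no further scan, case (b) applies without a no-death condition and gives the first iUPD date.

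**Step 6. Size of the gap**
If death comes before an on-schedule confirmatory scan, the gap can be a few days and is at most about 8 weeks. It is longer if that scan is missed, or if later scans stay at iUPD without confirmation (case c) before death.

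**Step 7. Parallel table**
Table 4 (iDOR) has the same layout and no-death condition, but its case (b) leaves out participant death, so the conflict does not arise there.

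**The case against.** The strongest reply is that the no-new-therapy block, applied as written, gives a single answer. A participant with iUPD, no iCPD and a recorded death meets only the death row, so the death clause is surplus wording and not a competing rule. That is correct. A reader might infer that this block gives one participant two different event dates. It does not, unless the clause is allowed to override its own header. The missed-scans row offers a second date only on the assumption in step 3.

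A reader might also infer that the same patient is dated differently under new therapy. The blocks are mutually exclusive, so the comparison is between two participants with the same sequence of scan and death. Some difference between blocks is also deliberate, since follow-up for iPFS stops at the start of new therapy. That design does not explain why iUPD reached before new therapy keeps its date when death follows, while the same sequence without new therapy does not.

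Third, it is tempting to read the 4-to-8-week confirmation window as the minimum size of the discrepancy. For a death before the confirmatory scan, 8 weeks is roughly a ceiling and there is no floor.

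Finally, the definitions in the SAP and the protocol do not settle which date is right. That stands, so the choice of rule below is a recommendation that follows the rest of Table 2.

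**Conclusion.** The point holds as an internal contradiction in Table 2. Two rows exclude death in the header and include it in the case list, and the literal result (date of death) disagrees with case (b), with the new-therapy iUPD row and, where it applies, with the missed-scans row. It also produces the anomaly that dying after iUPD yields a longer iPFS than declining scans.

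The consequence is small. The outcome is an event on either reading, and only its date changes, by the iUPD-to-death interval. iPFS is a secondary endpoint. After early termination the SAP plans no Kaplan-Meier estimate or test for it, only a listing. The documents do not show how many participants are affected. The study days in the working are assumed and illustrate the rule; they do not estimate an effect.

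**What to change.** State one rule for iUPD followed by death without iCPD, and state the order in which the rows of Table 2 apply. Preferably:

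- iUPD followed by death, with no iCPD and no intervening iSD, iPR or iCR: first iUPD date, event.
- Death with no outstanding iUPD: date of death, event, subject to the missed-scans rows.

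Remove the contradiction between the no-death header and the death clause in both the iUPD event row and the companion censoring row. Apply the same rule in the new-therapy and missed-scans rows, and say whether a missed-scan gap may end in death. This choice agrees with the table's own case list and needs the fewest changes elsewhere.

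The alternative is to delete the death clause from the two rows and declare that the death row governs. That is consistent within the block, but the new-therapy and missed-scans rows would then have to be changed to match, and the anomaly against participants who refuse scans would remain.

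Either way the cost is SAP wording only.

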**Table 4 iDOR Definition**

iDOR		
Situation	Date of Event or Censor	Outcome
Participant did not receive new anti-cancer therapy (ACT)		
iCPD	First date where iUPD criteria are met	Event
No iCPD nor death and NOT in one of the following cases : a) the participant stops protocol treatment because they were not judged to be clinically stable, b) no further response assessments are done (because of participant refusal, protocol non-compliance); c) the next timepoint responses are all iUPD, and iCPD never occurs;	Date of last radiological assessment	Censor
No iCPD nor death and is in one of the following cases : a) the participant stops protocol treatment because they were not judged to be clinically stable, b) no further response assessments are done (because of participant refusal, protocol non-compliance); c) the next timepoint responses are all iUPD, and iCPD never occurs;	First date where iUPD criteria are met	Event
Participant received new anti-cancer therapy (ACT)		
No progression before new ACT	Date of last radiological assessment before start of new ACT	Censor
iCPD before new ACT	First date where iUPD criteria are met	Event
iUPD before new ACT and NOT in one of the following cases : a) the participant stops protocol treatment because they were not judged to be clinically stable, b) no further response assessments are done (because of participant refusal, protocol non-compliance); c) the next timepoint responses are all iUPD, and iCPD never occurs;	Date of last radiological assessment before start of new ACT	Censor
iUPD before new ACT and is in one of the following cases : a) the participant stops protocol treatment because they were not judged to be clinically stable, b) no further response assessments are done (because of participant refusal, protocol non-compliance); c) the next timepoint responses are all iUPD, and iCPD never occurs;	First date where iUPD criteria are met	Event
Missed <math>\geq 2</math> scheduled radiological assessments		
If last assessment prior to missing $\geq 2$ scans is iUPD	First date where iUPD criteria are met	Event
If last assessment prior to missing $\geq 2$ scans is not iUPD and no progression after missing $\geq 2$ scans	Date of last radiological assessment	Censor

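### SAP Tables 2 and 4: the event rows for participants without new anticancer therapy omit the iUPD condition, so a participant with no iUPD who stops scanning becomes an Event with no date

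*SAP*

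**What the plan says.** SAP Section 5.1.2.5 defines iPFS as time from first dose "until death from any cause or radiographic disease progression assessed per iRECIST by investigator assessment". If stable disease or a response follows an iUPD, "iUPD status will be disregarded for determination of iPFS".

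Table 2 puts this into rows. In the block for participants who received no new anticancer therapy, those with neither confirmed progression (iCPD) nor death fall into two rows:

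- Event, dated "First date where iUPD criteria are met", for "No iCPD nor death and is in one of the following cases". The cases are (a) stopping treatment because not judged clinically stable, (b) "no further response assessments are done (because of participant refusal, protocol non-compliance, or participant death"), and (c) later timepoints that are all iUPD without confirmation.
- Censored at the last radiological assessment, for "No iCPD nor death and not in one of the following cases".

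In the block for participants who did receive new therapy, the corresponding Event row opens differently: "iUPD before new ACT and is in one of the following cases". A separate row there censors participants with no progression before the new therapy.

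Table 4 repeats the arrangement for iDOR. Its case (b) reads "no further response assessments are done (because of participant refusal, protocol non-compliance"), and its no-new-therapy rows again name no iUPD.

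**The concern.** Refusal or non-compliance satisfies case (b), and stopping treatment as clinically unstable satisfies case (a), whether or not an iUPD was ever recorded. A participant with at least one evaluable post-baseline scan, no iUPD, and either of these exits is therefore routed to the Event row. The date cell then points to something that is not in the data.

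A programmer working from the table has to depart from it. Two programmers could do so differently, by censoring at the last scan, by placing an event at the last scan, or by leaving the date missing. The listed status for iPFS and iDOR would then depend on an undocumented choice and could disagree with the PFS and DOR listings for the same person without explanation.

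**Working it through.** **1. Rows side by side.**

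| Block (Tables 2 and 4) | iUPD required for the Event row? | Row that censors a participant with no progression |
|---|---|---|
| No new therapy | No | Only if in none of cases (a) to (c) |
| New therapy | Yes | Yes, a row of its own |

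The list of cases is the same in both blocks of each table. Only the opening condition differs. Table 2's no-new-therapy row also includes participant death as a reason inside case (b), although the row is restricted to participants who have not died. That is a second sign that its wording was not reconciled.

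**2. Inputs for worked histories.** From the SAP: scans every 56 days; missing two scans means a gap between two imaging assessments of more than 2.5 × 56 = 140 days (the product reproduces the SAP's figure); iPFS = event or censor date − first dose date + 1; iDOR = event or censor date − first response date + 1. Assumed here: first dose on Day 1, scans on Days 57 and 113, then refusal, with no death and no new therapy, and a data cutoff on Day 365.

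**3. Results by history.**

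| Scans on Days 57, 113 | Event row read literally | Event row with an iUPD condition | Missed-scan rows, gap counted to cutoff | Missed-scan rows as the SAP defines the gap |
|---|---|---|---|---|
| iSD, iSD | Event, no date | Censor, Day 113 | Censor, Day 113 | Not triggered |
| iPR, iPR | Event, no date | Censor, Day 113 | Censor, Day 113 | Not triggered |
| iSD, iUPD | Event, Day 113 | Event, Day 113 | Event, Day 113 | Not triggered |
| iUPD, iSD | Event, no date if the iUPD is disregarded under 5.1.2.5; Event, Day 57 if it is not | Censor, Day 113 | Censor, Day 113 | Not triggered |

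The condition applied in the third column is an iUPD not followed by iSD, iPR or iCR.

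**4. Missed-scan gaps.** Counted to the assumed cutoff, the gap is 365 − 113 = 252 days, above 140. Counted between two scans, as the SAP defines it, the only gap is 113 − 57 = 56 days, so the rows do not apply to a participant who is never scanned again.

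**5. Durations once the condition is added.** For the stable participant, iPFS = 113 − 1 + 1 = 113 days, censored. For the responder, iPFS is also 113 days and iDOR = 113 − 57 + 1 = 57 days, both censored. If RECIST v1.1 reads the same scans as stable disease or partial response, Tables 3 and 5 also censor at Day 113, so the two sets of endpoints agree. The participant with an unresolved iUPD stays an Event at Day 113 and is unaffected.

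**The case against.** **The intent can be recovered.** Section 5.1.2.5 limits iPFS events to death and radiographic progression. The date cell presupposes an iUPD, case (c) does too, and the new-therapy rows state the condition outright. This is very probably a dropped qualifier. That stands as an account of what was meant. It does not make the row correct: its condition and outcome columns still give Event, and the censor row still excludes the participant.

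**The missed-scan block covers this participant.** Tables 2 and 4 each have a row that censors at the last radiological assessment when the last scan before missing two or more was not iUPD and nothing followed. On a natural reading it fits someone who stops scanning. That has weight, and it would be wrong to say that no row could censor them. But the footnote definition needs a second scan to close the gap. If it is set aside, two rows give opposite outcomes for one participant and the SAP does not say which prevails.

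**The consequence is limited.** This stands in full. SAP Sections 6.4.2.5 and 6.4.2.7 specify only listings for iPFS and iDOR, and a reader of the listing would notice an Event with a blank date.

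**Conclusion.** Wrong as written, and minor. The no-new-therapy Event rows in Tables 2 and 4 assign a status that contradicts Section 5.1.2.5 for iPFS, the parallel rows in the same tables, and Tables 3 and 5. Taken together with the missed-scan rows, the tables are at best self-contradictory.

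The effect is a wrong or undefined Event/Censor status and date in two listings of secondary endpoints. How many participants are affected cannot be stated, because the documents give no rate of refusal, non-compliance or stopping for clinical instability. The worked histories rest on assumed scan days and an assumed cutoff. The routing itself follows from the row wording and does not depend on them.

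A reader might infer two stronger things. One is that these participants are given a false progression date. They are not: without an iUPD the date is undefined. The other is that median or landmark iPFS and iDOR are biased downward. Protocol Section 9.4.2.3 did plan Kaplan-Meier estimates, but the SAP was written for an early-terminated study, covers only part of the protocol's analyses, and specifies no Kaplan-Meier output for either endpoint. Any such bias would also require placing the undated event at a particular time, such as the last scan, and the SAP states no such rule.

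**What to change.** In SAP Tables 2 and 4:

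1. Open both no-new-therapy rows (Event and Censor) with: *iUPD not followed by iSD, iPR or iCR; no iCPD; no death; and …* Section 5.1.2.5 already supplies the disregard rule for iPFS. Section 5.1.2.7 does not state it for iDOR, so the wording should bring it into Table 4 explicitly.
2. Add a row: *No unresolved iUPD, no iCPD, no death: censor at the last evaluable radiological assessment, whatever the reason scanning stopped.*
3. State which block takes precedence when scans are missed. Without this, the overlap with the missed-scan rows remains after the first two changes.

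The cost is wording in two tables, one condition in the derivation program and one sentence on precedence. No new data are needed, and participants with an unresolved iUPD keep their event and date.

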**Table 1 OS Definition**

Situation	Date of Event or Censor	Outcome
Death before or on analysis cutoff date	Date of death	Event
Death after analysis cutoff date	Analysis cutoff date	Censor
Last known alive is before or on cutoff date	Last known alive date	Censor
Last known alive is after cutoff date	Analysis cutoff date	Censor

OS = Date of Event or Censor – Date of First Dose +1

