**Table 3 PFS Definition**

PFS		
Situation	Date of Event or Censor	Outcome
No evaluable post-baseline imaging assessments, no death	Date of first dose (Day 1)	Censor
Participant did not receive new anti-cancer therapy (ACT):		
Radiographical progression documented per RECIST v1.1	Date of radiological disease progression	Event
No radiographical progression, but death recorded on eCRF	Date of death	Event
Neither radiographical progression nor death	Date of last disease assessment	Censor
Participant received new anti-cancer therapy (ACT):		
Radiographical progression documented per RECIST v1.1 after new ACT	Date of last radiological assessment before start of new anti-cancer therapy	Censor
Radiographical progression documented per RECIST v1.1 before new ACT	Date of radiological disease progression	Event
No radiographical progression before new ACT but death recorded	Date of last radiological assessment before start of new anti-cancer therapy	Censor
No radiographical disease progression nor death	Date of last radiological assessment before start of new anti-cancer therapy	Censor
Missed >=2 scheduled radiological assessments		
If radiographical progression or death occurs after missing 2 scheduled radiological assessments	Date of last radiological assessment before missing 2 scans	Censor

PFS = Date of Event or Censor – Date of First Dose +1

Missing 2 scheduled imaging assessments:

Missing 2 scheduled imaging assessments is defined as the gap between two imaging assessments as more than 140 days (2.5 times the scheduled imaging assessment interval (2.5 x 56 days)). Imaging assessments after first iUPD will be excluded in PFS derivation.

Note: Participant cannot be censored at “NE”. If NE is the only previous assessment, then PFS will be censored at Day 1.

To apply the cut-off date to PFS is to exclude those tumor assessments after cut-off date and anti-cancer therapy date after cut-off date in the analysis.

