#### **6.4.2.5 Analysis of Secondary Efficacy Endpoint: Progression-Free Survival per iRECIST (iPFS)**

iPFS data will be listed.

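### The cut-off notes for PFS and iPFS leave out deaths, so a death after the cut-off can be a PFS event while OS is censored at the cut-off (minor; listings only)

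*SAP*

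**What the plan says.** SAP 5.1.2.4, Table 1 (OS) has a row for "Death after analysis cutoff date" and censors it at the analysis cut-off date.

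For iPFS, the note under SAP Table 2 reads "To apply the cut-off date to iPFS is to exclude those tumor assessments after cut-off date and anti-cancer therapy date after cut-off date". For PFS, the note under Table 3 reads "To apply the cut-off date to PFS is to exclude those tumor assessments after cut-off date and anti-cancer therapy date after cut-off date". Neither note mentions deaths.

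The death rows for participants without new anti-cancer therapy are "No iCPD, but death recorded on eCRF" (Table 2) and "No radiographical progression, but death recorded on eCRF" (Table 3). Both give an event at the date of death, with no reference to the cut-off. When new therapy came first, the Table 3 row "No radiographical progression before new ACT but death recorded" censors at the last scan before that therapy.

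Both tables also censor a death that follows two missed scans, and the notes define the trigger: "Missing 2 scheduled imaging assessments is defined as the gap between two imaging assessments as more than 140 days".

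On output, SAP 6.4.2.5 says "iPFS data will be listed". SAP 6.4.2.4 and 6.4.2.6 say the same of OS and PFS.

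**The concern.** PFS and iPFS both count death as an event, so their data should be cut in the same way as the OS data. The notes apply the cut-off to two of the three kinds of date that decide PFS status and are silent on the third. The same death is then outside the data for OS and inside it for PFS.

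The partial cut has a second effect. Removing a therapy date after the cut-off moves the participant out of the block for those who received new therapy, where the death would not count, and into the block where it does. A record that would be censored becomes an event.

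At stake is whether the derived status and date for a participant in the PFS and iPFS listings are right, and whether they agree with the OS listing.

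**Working it through.** The plan gives no figure to reproduce. The check applies Tables 1 to 3 and their notes to hypothetical records. All days below are assumed study days. First dose is day 1, so the SAP formula (date of event or censoring − date of first dose + 1) returns the study day itself.

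**Record 1.** Last scan (stable disease) day 112, cut-off day 130, new therapy day 140, death day 200.

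- OS: 200 > 130, so Table 1 censors at day 130.
- PFS as written: the therapy date (140 > 130) is dropped. The participant falls in the no-new-therapy block with no progression and a recorded death, which is an event at day 200. iPFS reaches the same result through its own death row.
- Missed-scan rule: 200 − 112 = 88 days, below 140. It does not apply, even if the gap is read from scan to death.
- With no cut-off rule at all: therapy on day 140 precedes the death, so PFS is censored at day 112. For iPFS, the row for no progression before new therapy gives the same.
- With deaths after the cut-off also excluded: censored at day 112.

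**Further records.** Cut-off day 200. In every record the last scan on or before the cut-off is on day 169.

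| Record | OS | PFS as written | PFS with deaths also cut |
|---|---|---|---|
| A: no progression, no therapy, death 230 | censored 200 | event 230 | censored 169 |
| B: progression scan 225, therapy 228, death 260 | censored 200 | event 260 | censored 169 |
| C: therapy 180, death 230 | censored 200 | censored 169 | censored 169 |
| D: progression 169, death 230 | censored 200 | event 169 | event 169 |
| E: no progression, no therapy, death 320 | censored 200 | event 320 | censored 169 |

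A, B and E show the conflict. C and D do not, because therapy or progression before the cut-off already settles PFS.

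E depends on how the missed-scan definition is read. It is worded as a gap between two scans. Read as scan to death, 320 − 169 = 151 > 140 would censor E at day 169. That reading narrows the problem but does not remove it. Scans are due every 56 ± 7 days, so a participant on schedule has a last scan 0 to 63 days before the cut-off. Deaths up to 140 − 63 = 77 days after the cut-off, and at most 140 − 0 = 140 days after it, would still count as events.

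**The case against.** Four points can be made against this, and most of them limit its size.

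**No estimate is affected.** A reader might infer that follow-up extended only for those who die biases a PFS curve. Protocol 9.4.2.3 did plan Kaplan-Meier estimation. The SAP, written after early termination, replaces it with listings in 6.4.2.4 to 6.4.2.6. This stands: no planned estimate can be biased.

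**The situation may never arise.** The SAP refers to an analysis cut-off but gives no date. If the cut-off falls on or after the last recorded death, no record changes. This also stands. For the same reason, no frequency can be given. Protocol 2.2.2 offers only an upper bound on median survival (less than 15 months) for recurrent ovarian cancer. The documents give no interval between cut-off and database lock. The participants exposed are also only those still progression-free and not on new therapy at the cut-off, not everyone alive then.

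**PFS longer than OS is not a logical impossibility here.** OS censored at day 130 means survival of at least 130 days, and the participant in record 1 did live to day 200. This is right. The fault is that two endpoints for one participant use different data cuts, not that the result cannot occur.

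**The note does not say that deaths are kept.** A programmer might carry the Table 1 rule over to PFS. That is possible, but nothing in the SAP or protocol says so. The note sets out what applying the cut-off consists of, and the death rows have no cut-off condition. Followed literally, the text gives the inconsistent record, so this objection does not remove the point.

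**Conclusion.** The rule as stated is faulty, and the fault is minor. For PFS and iPFS, a death after the cut-off counts as an event at a date later than the censored OS time when three conditions hold: no progression by the cut-off, no new therapy by the cut-off, and no censoring by the missed-scan rule. If therapy starts after the cut-off and death follows, the notes turn a record that would be censored into an event.

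The consequence is confined to derived status and dates in listings, and it depends on at least one recorded death falling after a cut-off that the SAP does not define. The documents do not support a claim of biased survival estimates or any stated share of participants affected. The day values above are illustrations only.

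A likely source, though this is inference, is that the same note appears under the iDOR table. Death is not an event there, so the two exclusions are enough.

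**What to change.** Amend the notes under Tables 2 and 3 so that tumor assessments, new anti-cancer therapy dates and deaths after the analysis cut-off date are all excluded. The existing rows then treat such a participant as not having died and censor at the last evaluable assessment on or before the cut-off, or at day 1 if there is none, in line with Table 1. State the analysis cut-off date in the SAP, since it decides whether any record is affected.

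The cost is one phrase in each of two notes, one date and a matching filter in the derivation program. No new data are needed.
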